5.8.1 Study Compensation

Participants will be compensated for their participation at a rate of up to \$100 per visit (\$40 per patient-reported outcome, \$60 per in-person assessment visit) for a total of \$300 over the course of treatment. Those driving outside of Davidson County will also be offered either transportation assistance or compensation for mileage traveled on an as-needed basis.

5.9 Study withdrawal

Participants may withdraw from any part of the study at any time. If this occurs, only data collected prior to the time of study withdrawal will be kept for analysis purposes, except for the circumstance where the patient discontinues the intervention (such as for reasons outlined below) but wishes to complete follow-up assessments.

5.10 Treatment discontinuation

As per standard clinical procedures, a participant will be withdrawn from the treatment intervention if:

- Noncompliance to protocol, including but not limited to:
 - Participant engages in behavior that is disruptive,
 - Participant engages in behavior that interferes with the appropriate administration of treatment
 - Participant does not attend scheduled sessions
- The study must close for any reason
- Intercurrent illness or condition that would, in the judgment of the PI and mentorship team (including multiple MDs), affect assessment of clinical status to a significant degree or require discontinuation of study treatment
- General or specific changes in the participant's condition render the participant unacceptable for further treatment in the opinion of the PI and mentorship team
- The subject desires to withdraw

Participants who are withdrawn from the study treatment intervention will be invited to complete study assessments during treatment, post-treatment, 3-month and 6-month follow-up in order to allow for complete data for the planned intent-to-treat analyses. Participants will receive payment for the time it takes to provide outcome data at each assessment point.

5.11 Replacement of patients who discontinue early

The study intends that patients will complete the full 8 weeks of treatment. If a patient discontinues study treatment then that patient may be replaced with a new patient.

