5.4 Enrollment

We propose to enroll 96 participants in order to ensure complete data from 75 participants, assuming a very conservative 30% drop-out rate. We will monitor the dropout rate on an ongoing basis, and modify the number of participants recruited as needed to ensure a final sample of N = 75 study completers.

The study will enroll up to a total of 96 consecutive adults (aged \geq 18 years) with IC/BPS to participate in baseline and follow-up clinical assessment and quantitative sensory testing. Eligible participants will be randomized to an intervention (cognitive-behavioral self-management) or active control condition at a 2:1 rate. Following randomization, $\frac{2}{3}$ of participants will be provided with a cognitive-behavioral self-management intervention, and the other $\frac{1}{3}$ will engage in an active attention control condition. Those enrolled in the study will also be followed after the intervention time period of 8 weeks and again at 3 months.

The registration process will occur through VUMC either at the Osher Center for Integrative Medicine at Vanderbilt, located at [REDACTED], [name], online, or at the VUMC Clinical Research Center at [REDACTED], [name]. All participants will have a VUMC medical record identification number prior to beginning the study. Consenting will occur in-person or remotely where questions can be answered by a member of the research team, and assessment measures will be completed electronically on-site at VUMC or remotely online through a secure RedCap link. Consenting procedures will occur electronically in eConsent format online or on site using an electronic device where participants can fill out study measures online through RedCap. Psychophysical and Quantitative Sensory Testing will occur at the same site. After participants enroll in the study and complete their pre-treatment assessment, they will be randomized to the treatment or control condition.

For aims 2 and 3, we anticipate enrolling our first patient in the second half of the study’s first year. Given our recruitment strategies, we anticipate consistent enrollment of subjects in years 1 (N=10), 2 (N=43), 3 (N=43) of the project, peaking in years 2 and 3. We aim to reserve the majority of year 4 to conclude data collection and focus on data analysis, manuscript preparation, and additional grant

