9. STATISTICAL CONSIDERATIONS

9.1 Analytic Plan by Aim

Aim 1: To construct a patient-centered CBT self-management (SM) intervention specific to IC/BPS. Pre-work for this aim will include a theme analysis of coded transcripts from focus groups using NVivo 9 to code, analyze, and interpret transcripts using elements of grounded theory.⁷⁸ For the project period, this aim will primarily involve consolidating qualitative work and will use descriptive statistics where appropriate.

Aim 2: To obtain preliminary data comparing the effectiveness of integrating SM interventions into usual treatment (N = 50) to control (AC, N = 25) in improving targeted primary (symptom improvement [≥ 7 point reduction in GUPI]) and secondary (pain, distress, quality of life) outcomes.

Power and sample size considerations: ■ are comparing GUPI-Total Score, a continuous variable, between the SM group and a matched AC group with a 2:1 randomization scheme. The GUPI-Total Score tends to be normally distributed with a standard deviation of 8.61.^{47,79} A 7-point decrease in total GUPI score is considered clinically meaningful⁷⁹ and a robust assessment of response to treatment.⁴

Assuming a Type I error of 0.05 and power of .90, we will need 50 experimental subjects and 25 control subjects to reject the null hypothesis that the sample means of both treatment groups are equal post-treatment. ■ intend to have 50 experimental and 25 control subjects to obtain even groups for analytical purposes, as recommended by ■ DSBM. Given our use of statistical models, ■ power is increased when ■ appropriately adjust for covariates.

■ will test the hypothesis that those receiving the SM intervention will show improved outcomes relative to AC. ■ will use generalized linear mixed models to compare responses on the Genitourinary Pain Index (GUPI⁸⁰-Primary Outcome) between treatment groups, adjusting for baseline GUPI and covariates. As recent evidence recommends the examination of pain and urinary symptoms separately,²⁵ ■ will examine the GUPI pain subscale and GUPI urinary subscale separately in secondary analyses. ■ will perform one interim analysis at approximately 50% completion of data collection using the O'Brien-Fleming method to preserve alpha accounting for repeat testing.

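### Replacing treatment discontinuers and recruiting to 75 completers, with no analysis set in 9.1, is inconsistent with the intent-to-treat analysis named in 5.10 and could bias the SM-AC contrast in either direction

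*Combined protocol and SAP*

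**What the plan says.** All references are to the combined protocol and SAP.

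- **5.11** sets the replacement rule: "If a patient discontinues study treatment then that patient may be replaced with a new patient". The trigger is stopping treatment, not lacking an outcome.
- **5.10** lists the grounds for withdrawal from treatment, one of which is "Participant does not attend scheduled sessions". It then provides for continued assessment: "Participants who are withdrawn from the study treatment intervention will be invited to complete study assessments during treatment, post-treatment, 3-month and 6-month follow-up". The reason given is "in order to allow for complete data for the planned intent-to-treat analyses". This is the only place where intent-to-treat is mentioned.
- **5.9** says that after withdrawal from the study "only data collected prior to the time of study withdrawal will be kept for analysis purposes", with an exception for someone who stops the intervention but wishes to complete follow-up.
- **5.4** says the team will monitor dropout and "modify the number of participants recruited as needed to ensure a final sample of N = 75 study completers". The sentence before it, like 5.1, expresses the target as complete data on 75 participants.
- **9.1** gives the sample size: "Assuming a Type I error of 0.05 and power of .90, we will need 50 experimental subjects and 25 control subjects". It plans mixed models for GUPI adjusted for baseline and covariates. It names no analysis set and no method for missing GUPI, and does not mention intent-to-treat.
- **5.3** randomises 2:1 by stratified permuted blocks, without blinding. It does not mention replacements.

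**The concern.** The sections point to two different primary analyses. Someone working from 5.4, 5.11 and 9.1 would recruit until 50 SM and 25 AC participants had completed, and analyse those 75. Someone working from 5.9 and 5.10 would analyse everyone randomised, which the plan expects to be up to 96. Nothing fixes the choice in advance. Because allocation is unblinded and 9.1 plans an interim analysis, the choice could end up being made with knowledge of the results.

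The difference matters because discontinuation happens after randomisation and can depend on the arm. SM consists of therapist sessions with skills modules (5.6.1), and AC of scripted telephone questionnaires (5.6.2). People may leave these for different reasons. If those who leave are substituted, the groups compared are no longer the groups randomised. A second route to the same problem is allocation: if a replacement is placed in the vacated arm, that assignment bypasses the stratified list.

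The affected share need not be small. The plan itself allows for 30% dropout, and at that rate 96 enrolled would leave 96 x 0.70 = 67 participants, so the clause in 5.4 on raising recruitment would come into play.

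**Working it through.** **1. The plan's own figure.** Inputs from 9.1: SD 8.61, a 7-point difference (stated as the clinically meaningful decrease, taken here as the between-group difference), alpha 0.05 (two-sided assumed; the plan does not say), power 0.90, groups of 50 and 25.

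- Standard error = 8.61 x sqrt(1/25 + 1/50) = 2.109.
- Noncentrality = 7 / 2.109 = 3.32 on 73 degrees of freedom.
- Two-sample t-test power = 0.906 at 50/25 and 0.894 at 48/24.

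So 50/25 is the smallest 2:1 design that reaches 0.90. The 75 needed for power in 9.1 and the 75 completers in 5.4 are the same 75 people.

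**2. Bias if discontinuers are left out.** Let p be the share of an arm that discontinues, and g the amount by which completers in that arm improve more than its discontinuers would.

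- Mean improvement of everyone in the arm = completer mean - p x g.
- A completer analysis therefore overstates that arm by p x g.
- Bias in the SM-AC contrast = p_SM x g_SM - p_AC x g_AC.

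The formula has no fixed sign:

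- Equal p and equal g in both arms: bias = 0.
- Selective discontinuation in SM only: bias favours SM.
- Selective discontinuation in AC only: bias of the same size favours AC.
- All randomised analysed as assigned: replacement itself adds no bias.

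**3. Illustration.** The documents give neither p by arm nor g. Assume p = 20% or 30% in one arm only, g = 3 to 7 points, no selective loss in the other arm, and no true effect. Type I error is from the noncentral t with 50/25, SD 8.61, two-sided 0.05.

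| p | g (points) | Bias = p x g (points) | Type I error |
|---|---|---|---|
| 0.20 | 3 | 0.6 | 5.9% |
| 0.20 | 7 | 1.4 | 10.0% |
| 0.30 | 3 | 0.9 | 7.1% |
| 0.30 | 5 | 1.5 | 10.8% |
| 0.30 | 7 | 2.1 | 16.6% |

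The normal approximation gives 16.9% for the last row, so the range is about 6-17%. These are unadjusted t-test figures. The planned model adjusts for baseline GUPI and covariates, so its type I error under the same assumptions need not be identical.

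With selective loss in both arms, the terms offset. At p = 0.30 in one arm and 0.15 in the other, with g = 7 in both, the bias is 2.1 - 1.05 = 1.05 points.

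**4. Assessment times.** Section 5.1 has three assessments: before treatment, immediately after the 8 weeks, and 3 months later. Appendix O has no 6-month column. Section 5.10 offers withdrawn participants assessments during treatment and at 6 months as well. The post-treatment and 3-month assessments appear in both places; the other two appear only in 5.10.

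**The case against.** The strongest reply is that no section removes a replaced patient from the analysis. Section 5.11 is permissive, and enrolling more people to offset losses is compatible with intent-to-treat if everyone randomised is analysed as assigned. Sections 5.9 and 5.10 lean that way: they keep earlier data, let discontinuers complete follow-up and pay them for it, which would make little sense if they were to be discarded. Completer in 5.4 may only mean someone with complete data, since 5.1 and the preceding sentence of 5.4 say that. Section 5.3 makes no exception for replacements, so the default reading is that they are newly randomised.

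All of this stands, and it limits the point to what could happen. It does not remove it. Section 5.11 keys replacement to stopping treatment even when the outcome is available, 9.1 ties the analysis to the same 75, and the passages that favour retention are not carried into the analysis plan.

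A reader might infer that the rule favours SM because SM asks more of participants. The documents do not support that. Section 5.1 gives 50 minutes to each appointment in either condition, 5.6.2 describes a similar visit pattern for AC, and AC participants know their allocation and are held to a script, so they may be as likely to leave.

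**Conclusion.** The sections are inconsistent and should be reconciled. The replacement rule, the completer target and the missing analysis set together describe a completer sample, while 5.9 and 5.10 presuppose an analysis of everyone randomised. The consequence is a possible bias of unknown sign. It requires that replaced patients be left out while discontinuation differs by arm in rate or prognosis, or that replacements be put into the vacated arm.

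The 0.6-2.1 points and 6-17% type I error describe selective loss in one arm only, on assumed values. They are not an estimate for this trial, and zero is within the plausible range. The documents do not support the stronger readings that the plan excludes replaced patients or that the result will be biased towards SM. The extra assessment times in 5.10 are a separate inconsistency and add nothing to the bias argument, because the post-treatment and 3-month assessments are common to both lists.

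**What to change.** - **9.1:** State that the primary analysis includes all randomised participants in the arm assigned, with T2 and T3 outcomes sought regardless of treatment status. Say how missing GUPI is handled.
- **5.11:** State that discontinued participants stay in the analysis, and that any added participant is newly randomised from the next position in the stratum list, not assigned to the vacated arm.
- **5.4:** Define the target as participants with the primary outcome, not treatment completers.
- **5.10:** Reconcile the during-treatment and 6-month assessments with the schedule in 5.1 and Appendix O.

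The cost is protocol wording. The effect estimate may be slightly smaller than among completers.

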6. RISK MINIMIZATION

Below we detail risks as they relate to different aspects of our study and efforts to minimize risk. █ categorize potential risks in regards to the screening, assessment and treatment period. Risks related to privacy and confidentiality are also reviewed.

6.1 Screening Procedures

Regarding the telephone screening, research team members will follow an IRB-approved script informing patients of the study purpose and inclusion/exclusion criteria. If participants complete screening procedures online, they will answer the same series of structured questions and be provided with crisis services information embedded in the questions online. Research team members will also follow an IRB-approved in-person screening script if recruiting in person. Participants who indicate that they are having thoughts of self-harm or suicide will be provided with resources for follow-up immediately (i.e. the telephone number to the National Crisis Hotline and website www.suicidepreventionlifeline.org to chat with support staff online, and PI office number). Additionally, if this occurs in person or over the telephone, the RA will inform the PI, who will also follow-up with the potential participant within 24- 48 hours to assess if further assistance or referrals are necessary in order to provide adequate support. These resources will also be available online for those completing screening procedures electronically. The PI will provide a direct phone number to call during business hours for participant use for additional support and to make any necessary referrals. These participants will be ineligible for study participation. We have

successfully implemented these screening procedures in ongoing projects [REDACTED]
[REDACTED]).

6.2 Self-report assessments

Regarding the assessment battery, participants may experience temporary physical discomfort from prolonged sitting and/or temporary emotional discomfort answering questions about current emotional states and pain levels. To mitigate this risk participants will be informed that they do not have to answer any questions they feel uncomfortable answering. Further, participants may take as much time as needed to complete the assessments.

There is potential risk for transient emotional discomfort following answering questions about pain, psychological health, and overall wellness. During screening procedures, any individual with acute emotional distress will not be eligible for study participation, which minimizes this risk.

6.3 Psychophysical (QST) assessments

Risks associated with quantitative sensory testing are minimal. Participation in psychophysical testing is optional to participants. The procedure is designed to elicit the perception of pain, discomfort, or unpleasant sensations on various bodily quadrants. Participation may elicit these sensations for a brief period but this does not result in prolonged pain. Subjects will experience brief, moderate intensity acute pain upon application of the ischemic and thermal pain stimuli use both for acute pain evaluation and conditioned pain modulation assessment. However, subjects have total control over the duration of their exposure to this pain because they terminate the task by indicating when they have reached their tolerance limit. There are established protocols with limits of thermal temperature, which maximum temperature elicited is 127 degrees Fahrenheit. QST protocols have been reviewed extensively,⁷⁶ deemed a valuable measure of central and peripheral sensitization, and determined to be safe and do not stimulate pain crisis.⁷⁷ Additionally, participants are provided with instructions that testing can stop at any point in time. Previous research indicates that these tasks are safe, with safety of the thermal task further insured by a hardware cutoff in the TSA-II equipment that immediately cools the heat stimulus if a temperature greater than 51 deg C is reached (i.e., below the temperature at which tissue damage occurs). Because subjects have total control over the duration of the task, its psychological impact is expected to be minimal. At VUMC, both acute pain tasks have been used previously in numerous studies involving both chronic pain patients and healthy controls without incident, including work by [REDACTED].

6.4 Collection of biological samples

Collection of blood may be associated with pain or bruising at the venipuncture site. Further, individuals may in rare cases have a vasovagal response to needles or blood collection. All sample collection will be conducted with trained nursing personnel present to provide any additional support should this occur. Further, patients will be positioned in a seated or laying down position when providing blood samples to reduce risk. Participating in the collection of biological samples is optional to participants.

6.5 Treatment phase

The control condition will involve participants being asked about their health, symptoms and current functioning and oral administration of validated self-report assessments via telephone. This also may

produce temporary emotional discomfort in answering questions about pain and emotion, or temporary physical discomfort from prolonged sitting. In the same vein, participants will be informed they do not have to answer any questions that make them uncomfortable, and will be free to move around as needed to alleviate or prevent physical discomfort when speaking with study personnel.

Participating in self-management interventions with a psychologist can at times produce emotional discomfort as therapists can assist patients through encountering and approaching avoided tasks and emotions. Psychologists adhere to clinical judgment and ethical principles of nonmaleficence and beneficence and have patients' best interests and collaboratively established treatment goals in mind when engaging in treatment with participants. Participants choose how, when, and which goals to work toward with the assistance of the therapist. Participants are also free to withdraw from the intervention or control condition at any time.

In the event than an individual does not express any distress during screening but does so during visits with an interventionist, interventionists will operate by ethical guidelines established by the psychology profession and State of Tennessee Board of Examiners in Psychology to ensure and prioritize patient safety. Risk will be minimized of this event with the screening procedures in place to assess for acute emotional distress prior to enrollment.

6.6 Privacy and Confidentiality Issues

Only persons directly involved in the study will have access to written or electronic study data identifying individual patients. All research assistants will complete training in the responsible conduct of research prior to engaging in the study.

Informed consent will be obtained electronically for each participant in the study prior to their participation. Assessment data will be entered and stored using RedCap/SPSS in encrypted files on an encrypted laptop computer belonging to the PI. Participant tracking information will be stored on a separate password-protected excel file only accessible to the PI and a research team member. Participant tracking information, along with all study-related documents and files can also be stored in VUMC Box. They will be given a unique number, with tracking information of this number only accessible to the PI and members of the research team. A limited data set, containing no identifying information, may be shared with collaborating individuals at regional institutions. Such individuals will have signed Data Use Agreements with VUMC and will abide by these contracts prior to having access to any such information.

When they occur, remote visits (enrollment procedures, study visits) will occur through the use of Zoom teleconferencing software. This is a HIPAA-compliant, password-protected teleconferencing software that is highly secure. This is the same system used for remote clinical VUMC visits and all trained interventionists and study team personnel have high familiarity with the technology.

Assessment and consenting data will be collected and stored primarily online in a secure server in a secure RedCap database. In the event that assessments are completed on paper (e.g. if a participant is not comfortable using a computer), paper assessment data will be coded and de-identified, and stored separately in a locked drawer at OCIM. To maintain confidentiality in this circumstance, the PI will store all financial reporting and consent forms in a separate locked drawer in her office. Assessment data will be entered and stored using RedCap in encrypted files on an encrypted laptop computer belonging to the

PI. Participant tracking information will be stored on a separate password-protected form only accessible to the PI and authorized members of the research team. Session recordings will be reviewed by the PI for the purpose of fidelity monitoring and then erased. Access to these data and other patient recruitment materials will be restricted to study personnel only.

